Exclusion criteria to participation in this study include:

- 5) Age < 18
- 6) Emergency surgery
- 7) Persons not capable of providing informed consent
- 8) Persons participating in any other research study involving an investigational drug or device or investigational surgical procedure that could interfere with the physiologic parameters being collected (for example, a study evaluating different anesthesia regimens that could confound study results).
- 9) Non English-speaking

2.2 - Hypothesis

It is hypothesized that the AirSeal® System will allow for lower CO₂ absorption rates than the Xcel® System. Furthermore, lower variance in pneumoperitoneal pressure will allow for less "over-pressure" events and peritoneal stretch, which may reduce postoperative pain. Pain will therefore also be assessed through self-report and post-operative pain medication usage (see Table 4 & Appendix A), and analyzed in comparison between both groups.

The term "over pressure" refers to times when the measured pressure in the peritoneal cavity exceeds the set pressure on the insufflator. In such cases, the standard insufflation systems will stop the flow of CO₂ into the abdomen through the port and will actively vent gas to reduce the pressure back to the set point (usually 10mmHg with a maximum of 20mmHg). This "over pressure" theoretically should not occur with the AirSeal® system because the lack of a valve on the port allows gas to escape immediately when the pressure rises (e.g. abdominal muscle contractions when anesthesia is light) so that the pressure does not exceed the set level. "Peritoneal stretch" refers to stretching of the peritoneum (lining of the abdominal wall) from insufflation of the abdomen. The higher the pressure of the pneumoperitoneum/intra-abdominal pressure, the more stretch there will be of the peritoneum with potentially more postoperative pain.

We intend to analyze the results of a total of 100 patients randomized to either the AirSeal® system or conventional trocars.

2.3 - Study Variables & Outcomes of Interest

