The following data points are all routinely collected for patients who choose to undergo robotic prostatectomy, via the OhioHealth electronic medical record, CareConnect. We will collect similar data points for patients electing enrollment in this trial which include the following listed below (Tables 2-4). Data points which are not collected in the standard of care setting are noted below in **bold face type**. Only the study staff will have access to the database created solely for use in this study. Data will be de-identified following study completion, prior to statistical analysis.

Table 2. Study Variables by Operative Time-point

(a) Preoperative data [collected at the preoperative office/clinic visit, in the office setting, or in

the pre-anesthesia testing (PAT) office visit]:

- 1) Medical record number
- 2) Patient name
- 3) Patient date of birth
- 4) Phone number
- 5) Email address
- 6) Body mass index (BMI)
- 7) Weight (lb)
- 8) Medical history
- 9) Surgical history (major only)
- 10) Serum creatinine (most recent prior to surgery) (mg/dl)
- 11) Hemoglobin (g/dl)
- 12) Preoperative pain measured by the NRS-11 (Appendix A)**

(b) Intraoperative data:

- 1) Details of the surgical procedure
- 2) The number, size(s), and locations of ports used (standard protocol vs. deviation from standard protocol)
- 3) Values obtained from anesthesia report at baseline, 60 minutes after insufflations, and at the end of procedure and mean and standard deviation calculated from continuously recorded values:
 - a) End tidal CO₂ (mmHg)
 - b) O₂ saturation (%)
 - c) Respiratory rate
 - d) Blood pressure
 - e) Heart rate
 - f) Tidal volume (ml)
 - g) PIP (peak inspiratory pressure) (mmHg)
 - h) PEEP (positive end-expiratory pressure) (mmHg)
- 4) CO₂ absorption rate via arterial blood gases (ABGs) at baseline, 60 minutes after insufflations, and at the end of the procedure [PaCO₂ (mmHg), HCO₃ (mmol/L) & PaO₂ (mmHg)]
- 5) Number of times the anesthesiologist intervenes to adjust ventilation settings throughout the surgery to prevent the values from elevating further once they reach 37-38 mmHg
- 6) Estimated blood loss (EBL, in ml)
- 7) Core body temperature (after trocar placement, at 30 minutes, at 60 minutes, and at end of procedure; Fahrenheit)
- 8) Insufflation time (minutes)

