- 9) Insufflation pressure at which the procedure was performed (mmHg), and the total number (#), magnitude(s) (% increase in mmHg), and time(s) (hh:mm) of increased pressure episodes necessary to successfully complete the procedure
- 10) Procedure time (minutes from initial incision to closure)
- 11) Pneumoperitoneal pressure ranges (mmHg)**

12) Smoke evacuation quality at the end of surgery (1-Below Average; 2-Average Amount; 3-Above Average) (Appendix B)
 
13) Number of times significant loss of pneumoperitoneum occurs (#), timepoint, and level of pressure adjustment (mmHg)
 
14) Scope cleanings (#)
 
15) Malfunctions of the AirSeal® System or control devices (# times)
 
16) Total amount of gas used during the procedure (liters)

(c) Postoperative data collected in the PACU through discharge:
 
1) Postoperative pain by the NRS-11 at multiple time points (Appendix A)
 
2) Postoperative parameters (as recorded by the PACU nurses as standard of care)
 
a) O₂ saturation (%)
 
b) Time in PACU (post anesthesia care unit) (hours)
 
c) Post-operative nausea and vomiting (presence/absence)
 
d) Vital signs (HR/RR/BP/temp) – first recorded in PACU setting
 
e) Use of post-operative pain medication (ketorolac, Percocet, Tylenol Extra Strength), recorded as the total daily morphine equivalent dose (“MED”, in mg/day)
 
3) Incidence of wound infection
 
4) Length of stay (targeting same day or next day discharge; 0 to 2)

(d) Postoperative data collected through postoperative Day 1
 
1) Postoperative parameters (standard of care)
 
a) Vital signs (HR/RR/BP/temp) – first recorded in non-PACU setting
 
b) Use of post-operative pain medication (ketorolac, Percocet, Tylenol Extra Strength), recorded as the total daily morphine equivalent dose (“MED”, in mg/day)
 
2) Serum creatinine (mg/dl)
 
3) Hemoglobin (g/dl)
 
4) Urine output (ml; 1900-0700 hours postoperatively)
 
5) Incidence of wound infection

For item (b)2, a deviation from the standard port number/size(s)/locations would be due to body habitus, and will not have an effect the clinical outcomes for the patient. We will collect information on all surgical outcomes that occur until discharge from the PACU. The average amount of time spent in the PACU is roughly 1-2 hours. There will be no extended or long-term follow-up.

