Since the anesthesiologist will be adjusting ventilator settings at 37-38 mmHg to typically keep the end tidal CO₂ below 40 mmHg, we expect that there will not be a large amount of difference between standard and valve-less trocars regarding the ABGs. However, the ABGs will change over time, warranting the alteration of ventilator settings by the anesthesiologist. In other words, if the ABGs are same between the two groups but the anesthesiologist had to increase the respiratory rate or tidal volume to keep end tidal CO₂ low more so in the standard group than the valve-less, then we will conclude that the valve-less was better. Essentially, the ABGs are a sort of "control" whereby even if they are not different, it still allows us to know whether or not there was a real physiologic difference occurring, whether or not we saw a difference in the other measures that were adjusted in real time.

Table 4. Pain monitoring schedule by Pre-op and PACU RNs using NRS-11.

Timepoint	Definition
Baseline	Prior to surgery
Post-operatively	After surgery & after anesthesia completion
30 minutes post-operatively	30 minutes after surgical completion time (+/- 5 minutes)
60 minutes post-operatively	60 minutes after surgical completion time (+/- 5 minutes)
At discharge	Immediately prior to discharge from the PACU

Postoperative (post-anesthesia) pain will be evaluated at baseline, post operatively, once every thirty minutes for the first hour and every 8 hours until discharge (Table 4). Floor nurses (preoperative and PACU) will record pain scores reported by patients during structured interviews using an 11-point numerical rating scale (NRS-11), in which a rating of 0 corresponds to no pain, ratings of 1-3 indicate mild pain, 4-6 indicate moderate pain, and ratings of 7-10 correspond to severe pain (Appendix A).

Data will be collected using the forms in the Appendix. Data will be collected by a member of the research team (clinic nurse or clinical research coordinator). All data will be coded by subject number and de-identified. The designated clinical research coordinator will hold the key to subject codes in a locked cabinet and password-protected electronic file. Case reports formed with the coded key will be available only to the study staff.

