- General or specific changes in the subject's condition that render further treatment unreasonable or unsafe within the standards of clinical practice in the judgment of the Principal Investigator or treating physician

2.5 – Statistical Analysis

We will first compare the demographic and pre-operative clinical characteristics of the conventional and valve-less trocar groups to evaluate randomization fidelity. If any characteristics are found to be statistically significant between the groups, this will be accounted for in the analyses of the primary and secondary outcomes. We will describe all categorical variables as percentages and continuous variables with means and standard deviations.

Aim #1) Describe the perioperative CO₂ absorption rates between the conventional and valve-less trocar groups via the end-tidal CO₂ and PaCO₂ , at baseline, 60 minutes intraoperatively, and immediately following surgery. We will also examine the valve and valve-less trocar groups on their ability to maintain acceptable ABG levels by comparing the number of interventions required by the anesthesiologist during the procedure between groups.

We will describe the change in CO₂ and PaCO₂ levels at 3 intervals: baseline to 60 minutes, 60 minutes to end of surgery, and baseline to end of surgery to examine the trends in both groups. We will compare the conventional and valve-less trocar groups on the number of interventions required by the anesthesiologist to maintain acceptable pressure using Poisson regression. If a significant number of patients required no intervention we will use a zero-inflated model. Statistical significance will be set at p<.05. We will also compare CO₂ absorption rates between high pressure (>8mmHg) and low impact (≤8mmHg) procedures.

Aim #2) Compare the maximum pneumoperitoneal pressure (mmHg), smoke evacuation quality (categorical), and overall operative times (minutes) between the conventional and valve-less trocar groups.

We will compare the conventional and valve-less trocar groups on maximum pneumoperitoneal pressure and overall operative time using t-tests or Wilcoxon rank sum tests. We will compare the groups on evacuation quality using a chi-square test. Statistical significance will be set at p<.05.

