Aim #3) Compare pain scores through discharge from the preoperative and post-anesthesia care units (PACU) by monitoring self-reported pain ratings using an 11-point numerical rating scale (NRS-11) and pain medication usage via morphine equivalent dose (MED) units.

To evaluate our this outcome we will use a linear mixed model with pain score as the dependent variable and treatment group and time as independent variables. Mixed models are often preferred over a two-way ANOVA because they allow for incomplete data from participants and do not require a strictly normal distribution in the dependent variable. We will also examine the difference in MED units between groups using a t-test. Statistical significance will be set at p<.05.

[figure not shown]

3.0 - REFERENCES

- 2) McCarus SD, et al. Gynecological laparoscopy: improving laparoscopic herniation outcomes without trocar site fascial closure: a multicenter trial. Presented at: American College of Surgeons 90th Annual Clinical Congress; October 10-14, 2004: New Orleans, LA.
- 3) Ethicon Endo-Surgery. "Endopath Xcel Bladeless." *Xcel Bladeless*. Endopath, 2010. Web. 18 Sept. 2012. <<http://www.ethiconendosurgery.com/xcelbladeless>>.
- 5) A new Valve-Less Trocar for Urology Laparoscopy: Initial Evaluation. *Journal of Endourology* 2009;23: 1535-39.
- 6) Herati et al. Use of the valveless trocar system reduces carbon dioxide absorption during laparoscopy when compared with standard trocars. *Urology* 2011; 5: 1126-1130.

4.0 - APPENDICES

A. Numerical Rating Scale (NRS-11)

Pain monitoring schedule by RN in PACU using NRS-11.

Timepoint	Definition
Baseline	Prior to surgery
Post-operatively	After surgery & after anesthesia completion

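### The pain mixed model names only group and time while the pain series includes the preoperative score, so the group effect is diluted by about 20% on the Table 4 schedule and baseline precision goes unused

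*Combined protocol and SAP*

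**What the plan says.** Section 2.5, Aim #3, describes the pain model as a "linear mixed model with pain score as the dependent variable and treatment group and time as independent variables". It adds that mixed models are often preferred to a two-way ANOVA because they allow incomplete data. It does not mention an interaction, a contrast, a covariance structure or a baseline covariate.

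The preoperative score belongs to the same series. Aim #3 compares scores from the preoperative unit through the PACU. Table 4 and Appendix A list five time points: before surgery, after surgery and anesthesia, 30 minutes, 60 minutes, and "Immediately prior to discharge from the PACU". Table 2(a), item 12, confirms that preoperative NRS-11 is collected.

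The opening paragraph of Section 2.5 gives the only rule on baseline variables, and applies it to primary and secondary outcomes alike: "If any characteristics are found to be statistically significant between the groups, this will be accounted for in the analyses".

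The text below Table 4 describes a different schedule: "Postoperative (post-anesthesia) pain will be evaluated at baseline, post operatively, once every thirty minutes for the first hour and every 8 hours until discharge". Section 2.3 also says: "The average amount of time spent in the PACU is roughly 1-2 hours".

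**The concern.** The pain hypothesis in Section 2.2 is that fewer over-pressure events and less peritoneal stretch will occur with the valve-less device, "which may reduce postoperative pain". The quantity of interest is therefore a difference after surgery. A model with group and time as its only terms gives one group coefficient for the whole series. If the pre-surgery score is a row of the outcome, that coefficient mixes the postoperative differences with one the device cannot have caused, and it is pulled toward zero.

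The amount of pull depends on how many scores a patient has, and the plan does not fix that number. Baseline NRS, which could explain part of the between-patient variation, would enter as a covariate only after a significant imbalance. Under randomization that happens by chance about 5% of the time if the 0.05 level is used. In most realizations of this trial the baseline score would dilute the estimate and add no precision.

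**Working it through.** The documents give no effect size, SD, correlation or power for pain, so there is no stated figure to reproduce.

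**Inputs from the documents.** Five scores, one before and four after surgery (Table 4); 100 patients (Section 2.2); significance at 0.05 (Section 2.5).

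**Assumptions.** 1:1 allocation (50 per arm), two-sided testing, an equal effect d at all four postoperative times, and correlation 0.5 between postoperative scores.

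**Step 1: dilution with a random intercept.** With complete data and categorical time, each of n scores has weight 1/n. The expected baseline difference is 0, so the coefficient estimates d(n-1)/n.

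| Scores per patient | Coefficient | Dilution |
|---|---|---|
| 4 (60-minute and discharge scores coincide in a 1-hour stay) | 0.750d | 25% |
| 5 (Table 4) | 0.800d | 20% |
| 6 (one 8-hourly score added) | 0.833d | 16.7% |
| 7 (two added) | 0.857d | 14.3% |

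A simulation of 150 trials (50 per arm, intraclass correlation 0.5, true effect -1 at each postoperative time) gave a mean group coefficient of -0.81. A group-by-time model with the contrast taken over the four postoperative times gave -0.99.

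**Step 2: other covariance structures.** Let s be baseline SD divided by postoperative SD, and r the baseline-to-postoperative correlation. The mean of the four postoperative scores has variance m = (1 + 3 x 0.5)/4 = 0.625 in units of the postoperative variance. Under an unstructured covariance, generalized least squares gives the baseline row the weight (m - rs)/(s² + m - 2rs):

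- s = 1, r = 0.6: 0.025/0.425 = 6%
- s = 1.5, r = 0.3: 0.175/1.975 = 9%
- s = 1, r = 0.5: 0.125/0.625 = 20%
- s = 1, r = 0.3: 0.325/1.025 = 32%
- s = 0.5, r = 0.3: 0.475/0.575 = 83%

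Under a first-order autoregressive structure with correlation 0.2 to 0.8, the weight is 23% to 39%.

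**Step 3: power.** The per-patient variances are:

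- baseline-adjusted postoperative mean: m - r²
- unadjusted postoperative mean: m
- as written (random intercept): (s² + 8rs + 16m)/25, divided by 0.8² = 0.64 to put it on the scale of d

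Set baseline-adjusted power at 80%, so its standardized effect is 1.9600 + 0.8416 = 2.8016. The power of each alternative is Phi(2.8016 x sqrt(adjusted variance / its variance) - 1.96).

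| Case | Variances: adjusted / post only / as written | Power |
|---|---|---|
| s = 1, r = 0.5 | 0.375 / 0.625 / 0.9375 | 80% / 58.3% / 42.5% |
| s = 1, r = 0.3 | 0.535 / 0.625 / 0.8375 | 80% / 73.6% / 61.0% |
| s = 0.25 (SD 0.5 versus 2), r = 0.2 | 0.585 / 0.625 / 0.654 | 80% / 77.4% / 75.5% |

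In the first case, about 22 of the lost points (80 - 58.3) are unused baseline precision and about 16 (58.3 - 42.5) are dilution. In the third, dilution costs about 2 points.

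**Step 4: detectable difference.** With 50 per arm and an assumed SD of 2 NRS points, the difference detectable with 80% power is 2.8016 x sqrt(2 x 4 x variance / 50):

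- s = 1, r = 0.5: 0.69 / 0.89 / 1.09 points (adjusted / post only / as written)
- s = 1, r = 0.3: 0.82 / 0.89 / 1.03 points

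**The case against.** The strongest reply is that the sentence lists variables and is not a model formula. It presents the mixed model as the alternative to a two-way ANOVA, which usually carries an interaction. Table 2 also lists preoperative pain separately from postoperative pain, so baseline may not have been meant as an outcome row. Either reading could remove the dilution, and the plan excludes neither. But neither is written, and an interaction removes the dilution only for a contrast limited to postoperative times. No contrast is named, so the choice would be made after the data are seen.

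The power figures also rest on assumed SDs and correlations. If preoperative pain is low and varies little, the power loss is small, as the third case shows. That stands. The random-intercept estimate is still 20% too small in that case, and an unstructured covariance would give a low-variance baseline more weight.

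Omitting baseline adjustment in a randomized trial is a loss of efficiency and not an error in itself. There are also other valid repairs, such as keeping baseline as an outcome with the arm means constrained equal. Both points are fair.

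On the schedule, 1-2 hours is an average, and an 8-hourly rule might simply never apply to short stays. The mismatch with Table 4 is real all the same, and the dilution argument does not depend on it.

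**Conclusion.** The concern holds. On the plain reading of Section 2.5, the group coefficient for pain is diluted by 20% on the Table 4 schedule. This assumes a random intercept, complete data and a constant postoperative effect. Other score counts give 14.3% to 25%, and the unstructured examples run from 6% to 83%. The cost in power against a baseline-adjusted postoperative analysis ranges from about 4 to about 37 percentage points over the three cases, all resting on assumed SDs and correlations.

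The problem affects the size of the estimate and the power. It does not affect type I error. It concerns a secondary aim and does not threaten the main aim, but it should be corrected because the correction is nearly free and helps under every reading of the text.

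**What to change.** In Section 2.5, Aim #3:

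- Use only postoperative NRS scores as outcomes, with baseline NRS as a covariate whether or not the arms differ at baseline.
- Include arm, time as a category, and arm-by-time, and state the covariance structure.
- Name the arm difference averaged over the postoperative times as the pain contrast, with a 95% confidence interval. Report the time-specific differences as supportive.
- Add a one-line rule for a patient with no baseline score.

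In Section 2.3, reconcile Table 4 with the text below it and say which discharge is meant, so that the set of scores entering the model is fixed before analysis.

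The cost is three or four sentences and a few degrees of freedom. No new data are needed, because baseline NRS is already collected.
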